## **8. INTERVENTION DISCONTINUATION**

### Participant Withdrawal/Termination Criteria:

#### *Withdrawal/Termination criteria for Participants:*

Participants may be discontinued from just the study intervention (“Group Discontinuation”) OR both the study intervention and study assessments (“Study Withdrawal”) at any time.

Specific reasons for discontinuing a participant (“Group Discontinuation”) from the group are:

1. Voluntary discontinuation by the participant who is at any time free to discontinue his or her participation in the group, without prejudice to further treatment.
2. Safety reasons as judged by the investigator.
3. Substance use disorder or psychiatric symptoms worsen to a level that requires a higher level of care.
4. Revealing private information about other participants in the groups.

Specific reasons for withdrawing a participant (“Study Withdrawal”) from the entire study are:

1. Voluntary discontinuation by the participant who is at any time free to discontinue his or her participation in the study, without prejudice to further treatment.
2. Safety reasons as judged by the investigator.
3. Incorrect enrollment (i.e., the participant does not meet the required inclusion/exclusion criteria) of the participant.
4. Active severe substance use disorder or level of intoxication during study procedures that precludes ability to conduct assessments.

5. Participants unable to complete baseline assessments.

Participants who discontinue will be asked about the reason(s) for their discontinuation and the presence of any adverse events. If possible, they will be seen and assessed by the Principal Investigator. Serious and Unexpected Adverse events will be followed up.

If participants are terminated from group intervention for any reason (except incorrect enrollment or safety concerns that endanger the study team), then they will still be expected to complete their outcome assessments, unless the participant revokes informed consent and withdraws from study.

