## **9.5 Outcomes**

### **9.5.1 Primary Outcome**

Biochemically-confirmed opioid abstinence, which is defined as the number of two-week periods with a negative oral fluid test [negative for opiate, oxycodone, fentanyl, methadone] AND no self-reported illicit opioid use, based on weekly substance use self-report during the final 12 weeks (weeks 13-24) of the study (6 is the highest possible number of negative oral fluid toxicology screen time periods). Participants will be randomly selected to undergo a live-online supervised oral fluid screen at a rate of once every 2 weeks. Negative toxicology screens have been previously used to assess effectiveness of OUD treatment.

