9. CAT-DI
10. CAT-ANX
11. CAT-PSY
12. CAT-MANIA
13. CAT-SUD
14. CAT- PTSD
15. CAT-SDOH

## 9.6 Data Analyses

### **Primary Outcome:**

The **main primary outcome** is biochemically-confirmed illicit opioid abstinent periods (defined by a negative oral fluid test [negative for opiate, oxycodone, fentanyl, methadone] AND no self-reported illicit opioid use), during the final 12 weeks of the study (with 6 being the highest possible number of oral fluid tests during that time period).

Negative toxicology screens have been previously used to assess effectiveness of OUD treatment. We will use an intent-to-treat design to evaluate the extent to which M-ROCC impacts biochemically confirmed illicit opioid abstinence over 6 biweekly time periods during the final 12 weeks of the study, **using Generalized Estimating Equations (GEE)**, which accounts for the clustering of individual observations over time, with covariates. This analytic approach provides reliable estimates even when data are unbalanced. GEE is also robust against misspecifications of the working correlation matrix when specifying the correct dependent-variable distribution and canonical link function. The benefit of selecting the best correlation structure is the gains in efficiency. The Quasi-likelihood Under Independence Model Criterion (QIC) will be used to ensure the best fitting working correlation structure. **For dichotomous outcomes**, we will specify a binomial distribution and a logit link function, and robust standard errors clustered at the individual-level. For **missing data**, we will implement multiple imputation methods in Stata (mi procedure). This technique creates multiple complete datasets, imputes missing values using a probabilistic simulation method (e.g., chained equations),

analyzes each dataset, and uses standard rules to combine estimates and adjust standard errors for the uncertainty of imputation.

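### Section 8 lets substance use end outcome assessment under one rule and keeps it going under another, and the periods lost from the abstinence outcome are handled only by multiple imputation

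*Combined protocol and SAP*

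**What the plan says.** **Two routes out (Section 8).** Participants may leave the group only (Group Discontinuation), or leave "OR both the study intervention and study assessments" (Study Withdrawal).

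- Study Withdrawal, reason 4: "Active severe substance use disorder or level of intoxication during study procedures that precludes ability to conduct assessments".
- Group Discontinuation, reason 3: "Substance use disorder or psychiatric symptoms worsen to a level that requires a higher level of care".
- People terminated from the group for any reason, other than incorrect enrolment or a safety concern that endangers the study team: "then they will still be expected to complete their outcome assessments, unless the participant revokes informed consent and withdraws from study".

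**Outcome (Section 9.5.1).** A two-week period counts as abstinent if the oral fluid test is negative for the listed opioids "AND no self-reported illicit opioid use, based on weekly substance use self-report during the final 12 weeks (weeks 13-24) of the study". The score runs from 0 to 6.

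**Analysis (Sections 9.2, 9.3 and 9.6).** The primary comparison is by intent to treat in all randomised participants, using GEE. Multiple imputation in Stata is the only method given for missing primary data. Section 9.2 states that, because the analysis is by intent to treat, the primary outcome is not sensitive to how many people drop out after randomisation. The sensitivity analysis named for data collection (Section 5.1, Duration) concerns late surveys and excludes oral fluid screens.

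**The concern.** The primary outcome measures opioid use, and one reason for ending its measurement is substance use. Periods lost that way are unlikely to resemble the observed periods, even after allowing for earlier data. An intent-to-treat label does not protect against this: it fixes who is analysed, but not what is known about them.

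Section 8 also gives no way to tell which rule governs a participant whose substance use has become severe. Under Group Discontinuation reason 3 the tests and weekly surveys continue. Under Study Withdrawal reason 4 they stop. Such cases are foreseeable: Section 4.1 admits people with under 90 days of abstinence, and Section 7.2.1 lists worsening of the disorder and intoxication as expected risks. At screening, Sections 4.3 and 6.2.2 treat symptoms or intoxication from recent use as transient and allow a re-review after 30 days. Reason 4 has no such provision.

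At stake is whether the estimated arm difference describes abstinence in everyone randomised. The cocaine and benzodiazepine outcomes depend on the same tests.

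**Working it through.** **1. The plan's own figure.** Section 9.2 gives means of 4.67 (SD 1.23) and 4.11 (SD 1.27) negative tests of 6, 192 randomised (96 per arm), ICC 0.01 and cluster size 24.

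- Design effect: 1 + (24 − 1) × 0.01 = 1.23; 192 / 1.23 = 156.1, or 78 per arm.
- Pooled SD: √[(1.23² + 1.27²)/2] = 1.250; d = (4.67 − 4.11)/1.250 = 0.448.
- Power at d = 0.45 with 78 per arm: 80.2% (normal) or 79.7% (noncentral t).

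The planned power reproduces to within rounding. The step from 192 to 156 is clustering alone, with no allowance for missing outcome data.

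**2. Section 8 side by side.**

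| | Group Discontinuation, reason 3 | Study Withdrawal, reason 4 |
|---|---|---|
| Trigger | Disorder worsens, higher level of care needed | Active severe disorder, or intoxication, that precludes assessment |
| Outcome assessments | Continue | End |

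Study Withdrawal also ends the intervention. The continued-assessment sentence covers termination from the group for any reason, and reason 4 is not among its exceptions. Read literally, the section both ends and expects the assessments of the same person.

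**3. Illustration of size.** No withdrawal rate under reason 4 is given, so the inputs here are assumed. Let μ be the planned arm mean, w the fraction of the arm withdrawn, and a their true number of abstinent periods. Assume all six periods are missing and are imputed at the mean of the rest of the arm. Then

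estimated arm mean = (μ − w·a) / (1 − w).

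| Withdrawn of 96, M-ROCC v control | a | M-ROCC | Control | Difference | Change from 0.56 |
|---|---|---|---|---|---|
| 2 v 4 | 0 | 4.769 | 4.289 | 0.481 | −14% |
| 2 v 4 | 2 | 4.727 | 4.202 | 0.525 | −6% |
| 2 v 4 | 3 | 4.706 | 4.158 | 0.547 | −2% |
| 3 v 6 | 0 | 4.821 | 4.384 | 0.437 | −22% |
| 3 v 3 | 0 | 4.821 | 4.243 | 0.578 | +3% |
| 4 v 2 | 0 | 4.873 | 4.197 | 0.676 | +21% |

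First row: 4.67/(1 − 2/96) − 4.11/(1 − 4/96) = 0.481 (differences are taken before rounding). The sign follows the assumed imbalance, and the size follows a.

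**4. The other anchor.** Suppose instead that the planned means describe only those still measured. The imputed difference then stays at 0.56, and with a = 0 the true difference is 4.67(1 − w_M) − 4.11(1 − w_C). This gives 0.53 at 5% v 5%, 0.30 at 10% M-ROCC v 5% control, and 0.74 at 5% v 10%. Again the direction is open.

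**The case against.** **The trigger is narrow.** Withdrawal is permissive. The qualifier about precluding assessment may govern both halves of reason 4, in which case it reaches only people who could not be assessed anyway. A positive test or reported opioid use triggers nothing. A reader might infer that participants who fail the abstinence outcome stop being measured; the text does not say so. What stands is that one precluded assessment need not preclude later ones, and nothing provides for resuming them.

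**Reason 4 covers any substance.** The protocol's own examples of severe use in Sections 4.2 and 4.3 are alcohol and benzodiazepines, and such a person may be opioid-abstinent. This stands, and it makes 0 of 6 an extreme assumption.

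**The rules may be two tiers.** One turns on level of care and the other on ability to be assessed. That is a fair reading, but the section does not state it, and the continued-assessment sentence cuts across it.

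**Imputation may do better.** Chained equations could use a person's own earlier tests and weekly reports. This would reduce the bias but not reliably remove it, because the model is unspecified and does not name the withdrawal reason.

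**Uneven use by arm is not shown.** A reader might infer that unblinded staff choose between the rules. Section 6.2.3 lists the principal investigator as blinded and the coordinators as not. Section 8 names who decides group discontinuation but not who decides Study Withdrawal.

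**Conclusion.** The concern holds as a conflict within Section 8, joined to a missing-data plan that does not address it. Outcome collection can end for a reason likely to be related to the primary outcome. The lost periods go only to multiple imputation, and Section 9.2's statement that dropout does not matter is not justified for losses of this kind.

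The size and direction cannot be derived from the documents. The illustrative differences, from 0.44 to 0.68 against a planned 0.56, rest on assumed withdrawal counts, six missing periods per person, imputation at the arm mean, and 0 to 3 truly abstinent periods.

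Two stronger conclusions are tempting. One is that the rule dilutes the treatment effect by a known percentage. That needs more withdrawals in control: with a = 0, equal numbers widen the difference. Section 9.2's dropout ranges (17-28% and 21-44%) cannot supply the rate, because they describe dropout from the intervention, after which assessments are still expected. The other is that reason 4 should simply be deleted. Study Withdrawal also governs the intervention, so deletion would choose between stopping rules, which this point does not do.

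**What to change.** **Protocol, Section 8.** Reconcile reason 4 with Group Discontinuation reason 3 and the continued-assessment sentence, for outcome collection only. Oral fluid tests and weekly surveys should not end because of substance use unless consent is revoked or one of the section's existing exceptions applies. An assessment that cannot be done is recorded as missed and rescheduled where possible, and later scheduled assessments are still offered. Whether group participation stops stays with the investigators.

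**Analysis, Section 9.6.** Record the reason for each such missed period and report it by arm. Include the reason in the imputation model. Add a sensitivity analysis that counts these periods as not abstinent, or one that is delta-adjusted. Amend the Section 9.2 statement about dropout to match.

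**Cost.** A short amendment, some extra rescheduling contacts and one extra analysis. The means already exist: tests supervised by video, a make-up test within 24 hours for selected participants who miss group (Section 5.1), and outreach calls every two weeks (Section 6.2.4). Analysis alone would be a weaker remedy, since it cannot recover periods that were never measured.

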#### New Information

Any pertinent new information will be communicated to study participants via e-mail if they have an e-mail address, otherwise via phone, by the research coordinator. In light of new information, participants may elect to discontinue their participation in the study.

## **9. STATISTICAL CONSIDERATIONS**

### **b.**

#### **9.1 General Design Issues**

Retention can be a problem in OUD behavioral therapies studies. To support the attractiveness of the study and ensure outcome measure completion, we will provide \$5 gift cards for each week that a participant attends a group session and \$5 for each bi-weekly period in which all assigned surveys and toxicology screens have been completed. We will obtain phone number and email of 3 close contacts in the demographics form so that we can more easily reach participants who may not be attending study sessions. We will call participants every other week for brief engagement calls, which has worked to increase retention by 20% in previous studies and will call all participants who missed a session within 48 hours.

#### **9.2 Sample Size and Randomization**

##### Justification of Sample Size and Power Calculations:

This study will enroll an approximate of  $n = 236$  and maximum of  $n = 280$  participants who will sign informed consent and our power analyses have identified that we will have the sample to identify meaningful effects with an effective sample size of  $n=156$  with 78 individuals in the M-ROCC arm and 78 individuals in the control group. We expect to randomize at least 192 participants (96 M-ROCC: 96 Control) over 8 months in order to have an effective sample size of  $n=156$ . We will aim to recruit participants with an active buprenorphine prescription from providers in U.S. states approved for recruitment by the IRB to enroll patients at a rate of approximately 30 participants per month, anticipating 19% loss during screening and baseline assessments, so we can randomize approximately 24 participants each month for 8 months.

Based on R21 urine toxicology data, we will focus our primary outcome analysis on the impact of M-ROCC on opioid use starting 12 weeks after intervention assignment. We estimate a mean of 4.67 negative tests for all illicit opioids (opiates, oxycodone, fentanyl, methadone) out of 6 random oral fluid toxicology tests conducted during the last 12 weeks in M-ROCC (SD 1.23) ( $n=78$ ) and 4.11 negative tests for all illicit opioids in the control check-in group (SD 1.27) ( $n=78$ ). We anticipate an effect size of Cohen's  $d = 0.45$  for between-group difference in percentage of monthly positive toxicology screens. Participation of  $N=192$  individuals randomized (with an effective sample size of 156 with 78 individuals in the M-ROCC arm and 78 individuals in the control group) allows for  $> 80\%$  power to detect an effect size of 0.45 for negative toxicology for all illicit opioids between M-ROCC and control arms. This power calculation was generated assuming a t-test of the difference between two means, a 1:1 intervention to control recruitment ratio, a type I error of 0.05, a two-sided comparison, and a design effect of 1.23 derived from an ICC of 0.01 with 8 group clusters with average cluster size of 24, which represents the average number of people randomized in each monthly cohort to either live-online M-ROCC or the live-online control group. This level of cluster was selected because it will encompass cohort effects. As the primary outcome will be analyzed in an intent-to-treat analysis, it is not sensitive to the number of individuals who drop out of the study after randomization. For secondary outcomes, based on pilot data and other relevant studies, we anticipate dropout from intervention in M-ROCC between 17-28% at 24-weeks and dropout in the control groups of 21-44% at 24-weeks.

In previous primary care studies, we have reported the impact of MTPC over 24 weeks on reductions in anxiety as measured by the PROMIS-ASF as  $d = -0.72$  ( $n=81$ ),  $p<0.001$  and  $d = -0.80$ ,  $p<0.001$  ( $n=136$ ). In our recent R21 pilot study, we reported significant Anxiety reductions over 24 weeks among patients with co-morbid anxiety at baseline ( $\geq 55$  at baseline) ( $p < .05$ ,  $ES = -0.556$ ). Given the

likelihood of a small effect of control on Anxiety after 4 weeks of buprenorphine treatment, we anticipate an effect size of  $d = -0.56$  for between-group change in PROMIS-ASF.

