### Administration

Participants will be enrolled on a rolling basis in preparation for their randomization to either the live-online M-ROCC or live-online control arm. Initially, randomization will only occur once 24 patients are ready for randomization. Following this initial group, every 4 weeks if at least 24 participants have completed baseline measures and are ready to start a group, they will be randomized using randomly selected block sizes of 4, 6 and 8 with a 1:1 ratio (24 weeks of live online M-ROCC : 24 weeks of live online control group). Next, after randomization, the participant will be informed about their assignment and given a start week for group sessions (either live online control or live online M-ROCC LDM) and will be given information about the group and its structure with a start date scheduled. We will aim to recruit constantly, with a new M-ROCC and control group beginning every 4-5 weeks.

We will aim for participants to begin attending control or LDM groups as soon as possible after randomization, but at least within 4 weeks. The study timeline will start

with week 1 being the first week the participant is assigned to start the study assigned group. Participants will continue to participate in standard care at each site while awaiting randomization and group placement, as well as throughout their enrollment in the study. For both study arms, participants will verify their presence with the group leader or research coordinator who will take attendance each week, which will be transferred to REDCap by the research coordinator after group.

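### The design effect of 1.23 and effective sample size of 156 treat monthly cohorts holding both arms as the cluster; the cluster that matters is the single-arm therapy group, and power should be shown over its ICC

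*Combined protocol and SAP*

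**What the plan says.** Under Justification of Sample Size and Power Calculations (section 9.2), the power statement for the primary outcome rests on "a design effect of 1.23 derived from an ICC of 0.01 with 8 group clusters with average cluster size of 24". The plan explains that 24 is the average number randomised per monthly cohort to either arm, and gives its reason: "This level of cluster was selected because it will encompass cohort effects". The same section confirms the count: "so we can randomize approximately 24 participants each month for 8 months", which makes 192 in total, 96 per arm. From this it derives an effective sample size of 156 (78 per arm) and claims more than 80% "power to detect an effect size of 0.45 for negative toxicology for all illicit opioids between M-ROCC and control arms".

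The other inputs are "This power calculation was generated assuming a t-test of the difference between two means, a 1:1 intervention to control recruitment ratio" and "a type I error of 0.05, a two-sided comparison".

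Under Administration (section 5.1), participants who are ready are randomised every four weeks or so, 1:1, in random blocks of 4, 6 and 8. On group starts, that section says: "We will aim to recruit constantly, with a new M-ROCC and control group beginning every 4-5 weeks".

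**The concern.** The formula 1 + (m − 1) × ICC gives the variance inflation of an arm comparison when every member of a cluster is in the same arm, as in a cluster-randomised trial. Here each cluster of 24 is split about 12:12 by individual randomisation. Whatever raises or lowers outcomes for a whole month's intake acts on both arms and drops out of the difference. The stated reason for choosing this level, to capture cohort effects, names a source of correlation that does not cost precision in this design.

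The correlation that does cost precision is among people who attend the same group and so share an arm, leaders and peers. The plan gives no ICC for that level. The headline figure of 156 therefore describes a cohort-randomised trial, which this is not. A reader of section 9.2 cannot see how power depends on the ICC that matters.

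**Working it through.** **Inputs from section 9.2:** 192 randomised (96 per arm), 8 cohorts of 24, ICC 0.01, d = 0.45, two-sided alpha 0.05, two-sample t-test. Means are 4.67 (SD 1.23) and 4.11 (SD 1.27).

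**Input derived from sections 5.1 and 9.2:** one new M-ROCC group and one new control group per cohort, so 8 × 2 = 16 starting groups of 24 / 2 = 12. The plan does not state this number.

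**1. The plan's own figures.**
- Design effect: 1 + (24 − 1) × 0.01 = 1.23.
- Effective sample size: 192 / 1.23 = 156.1, or 78 per arm.
- Effect size: pooled SD = √[(1.23² + 1.27²)/2] = 1.250, so d = 0.56 / 1.250 = 0.448, which rounds to 0.45.
- Power at 78 per arm and d = 0.45: 80.2% by normal approximation, 79.7% by the non-central t.

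The arithmetic reproduces.

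**2. What a cohort-level ICC does to the arm difference.** With a total variance of 1 and a cohort effect of variance ICC shared by both arms, the cohort terms cancel. The variance of the arm difference is 2 × (1 − ICC) / 96, against 2 / 96 under independence. The ratio is 1 − 0.01 = 0.99, not 1.23. A simulation of 8 cohorts split 12:12 agrees, at about 0.98 to 1.00. Power at d = 0.45 would then be 87.7% (96 / 0.99 per arm, non-central t).

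**3. What a therapy-group ICC does.** These clusters lie wholly in one arm, so the formula applies with m = 12.
- Design effect: 1 + (12 − 1) × 0.01 = 1.11. Simulation gives about 1.11 to 1.12.
- Effective sample size: 192 / 1.11 = 173.0, or 86.5 per arm.

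**4. Power at d = 0.45 over the therapy-group ICC (m = 12).** The t-test is shown on two bases: individual-level degrees of freedom, and 16 − 2 = 14 degrees of freedom for a comparison at group level.

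| ICC | Design effect | Effective N | Power, individual df | Power, 14 df |
|---|---|---|---|---|
| 0.01 (plan's value) | 1.11 | 173.0 | 83.7% | 78.6% |
| 0.02 (assumed) | 1.22 | 157.4 | 80.1% | 74.7% |
| 0.05 (assumed) | 1.55 | 123.9 | 70.0% | 64.4% |

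**5. Where the plan's figure stops being conservative.** Groups of 12 reach a design effect of 1.23 at ICC = 0.23 / 11 = 0.021. Above that, 156 overstates the effective sample size.

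**6. Sensitivity to group size.** Section 5.1 gives 6 to 15 people for the intensive groups. At ICC 0.01 with individual-level degrees of freedom, power runs from 85.7% (m = 6) to 82.7% (m = 15).

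**The case against.** The plan discloses both what the 24 stands for and why that level was chosen. Its calculation is internally correct, so this is a mis-specified cluster level and not an arithmetic slip. At the stated ICC the choice is also conservative, because the corrected design effect is smaller. All of that stands.

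A reader might infer that the power claim fails because 78 per arm gives 79.7% and not more than 80%. The documents do not support that reading. The normal approximation gives 80.2%, and the plan expects to randomise at least 192. With 194 the non-central t already gives 80.2% at the plan's own design effect (97 / 1.23 = 78.9 per arm). The gap is rounding.

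The figure of 12 can fairly be challenged. The primary outcome covers weeks 13 to 24. By then M-ROCC participants may have repeated LDM, moved to MTPC-OUD or gone to MCS, so groups in that arm re-form and may mix cohorts. Sixteen groups of 12 describes the starting groups only.

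It is also fair that a flat replacement of 173 and 84% would not be safe. It would carry over an unsourced ICC that the plan attached to cohorts, and it would ignore the small number of groups. This is why the restated power has to be a range with its degrees-of-freedom basis given.

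**Conclusion.** The design effect of 1.23 and the effective sample size of 156 do not follow from this design. A cohort effect common to both arms gives a variance ratio of about 0.99. Correlation within single-arm groups of about 12 gives 1.11 and an effective sample size of about 173 at ICC 0.01, roughly 11% more than stated (173 / 156 = 1.11).

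It would be tempting to conclude that the trial is underpowered. The documents do not show that: at the plan's own ICC the error is on the safe side. The opposite inference, that power is simply about 84%, is not supported either. It holds only with individual-level degrees of freedom and a therapy-group ICC near 0.01. With 14 degrees of freedom the figure at the same ICC is 78.6%.

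The conclusion rests on one starting group per arm per cohort, equal groups of 12, and d = 0.45 as planned. ICCs above 0.01 are assumptions chosen to show the range.

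**What to change.** In section 9.2:
- Name the assigned therapy group as the cluster, about 16 starting groups of about 12, and say that this is approximate because M-ROCC participants can change groups.
- Restate the design effect as about 1.11 and the effective sample size as about 173 at ICC 0.01, and give the source of the ICC.
- Replace the single power figure with a range over the therapy-group ICC, stating the degrees-of-freedom basis: 83.7%, 80.1% and 70.0% at ICC 0.01, 0.02 and 0.05 with individual-level degrees of freedom, and 78.6%, 74.7% and 64.4% with 14.

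In section 9.6, add randomisation cohort as a fixed factor in the primary GEE, since randomisation is already carried out cohort by cohort. With 8 cohorts this costs about 7 degrees of freedom. It handles cohort effects only. It does not account for correlation within therapy groups, and the 14-degree-of-freedom figures above do not include it.

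The cost is a rewording of section 9.2 and one variable that the study already holds. No further participants or data are required.

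### Power for the primary outcome does depend on dropout: Section 9.2 makes no attrition allowance, and complete-data power at 192 randomised is already only about 80%

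*Combined protocol and SAP*

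**What the plan says.** Section 9.2 (Justification of Sample Size and Power Calculations) claims more than 80% "power to detect an effect size of 0.45 for negative toxicology for all illicit opioids between M-ROCC and control arms". The basis is stated: "This power calculation was generated assuming a t-test of the difference between two means", 1:1 allocation, "a type I error of 0.05, a two-sided comparison, and a design effect of 1.23 derived from an ICC of 0.01" and cohorts averaging 24. The outcome inputs are "We estimate a mean of 4.67 negative tests for all illicit opioids" out of six (SD 1.23) under M-ROCC, against "4.11 negative tests for all illicit opioids in the control check-in group (SD 1.27". The plan expects to randomise 192 and takes 156 (78 per arm) as the effective sample.

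The paragraph then says that, because the primary analysis is intent to treat, "it is not sensitive to the number of individuals who drop out of the study after randomization". The next sentence, introduced as applying to secondary outcomes, anticipates "dropout from intervention in M-ROCC between 17-28% at 24-weeks and dropout in the control groups of 21-44% at 24-weeks".

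Section 9.6 (Primary Outcome) analyses six biweekly periods by GEE. For missing data it says "we will implement multiple imputation methods in Stata (mi procedure"), with standard errors adjusted for imputation uncertainty. Neither Section 9.5.1 nor Section 9.6 scores an unobserved period as non-abstinent.

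**The concern.** Intent to treat settles who is analysed and in which arm. It does not supply a test that was never taken. A primary analysis would be unaffected by the number of dropouts only if a fixed rule gave every missing period a value, and the plan has no such rule. It imputes, and its own description of imputation accepts that missing values widen the standard error.

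The paragraph is also inconsistent with itself. Dropout is treated as relevant to the secondary outcomes, yet Section 9.6 handles anxiety, the main secondary outcome, with the same combination of intent to treat and multiple imputation. The combination cannot protect one and not the other.

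At stake is the power attributed to the primary comparison. With no attrition allowance, any net loss of weeks 13-24 data at 192 randomised takes power below the stated level, and readers of the plan are told that this cannot happen.

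**Working it through.** **Inputs (Section 9.2).** Means 4.67 and 4.11; SDs 1.23 and 1.27; two-sided alpha 0.05; 192 randomised, 96 per arm; ICC 0.01; cluster size 24; intervention dropout 17-28% (M-ROCC) and 21-44% (control); maximum enrolment 280, with 81% of those enrolled randomised (Précis).

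**1. Reproduce the plan's figure.**
- Design effect = 1 + (24 − 1) × 0.01 = 1.23.
- Effective sample = 192/1.23 = 156.1, or 78 per arm. Nothing else is deducted.
- Pooled SD = √((1.23² + 1.27²)/2) = 1.250; d = (4.67 − 4.11)/1.250 = 0.448.
- Power at 78 per arm: 79.4% (t-test, d = 0.448), 79.7% (t-test, d = 0.45), 80.2% (normal approximation, d = 0.45).

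The stated figure is reproduced to within rounding, and it is spent entirely on the design effect.

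**2. Let missing data cost information.** The plan states no rate of missing primary-outcome data, so the intervention-dropout rates are used here as an assumption. Let *k* be the share of the dropouts' weeks 13-24 information that is kept. Effective size per arm = 78 × (1 − dropout × (1 − *k*)). Power is from the noncentral t distribution with noncentrality d × √(n₁n₂/(n₁ + n₂)), d = 0.448 and design effect 1.23.

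| Dropout, M-ROCC / control | None kept (n₁, n₂) | Power | Half kept (n₁, n₂) | Power |
|---|---|---|---|---|
| 17% / 21% | 64.7, 61.6 | 70.5% | 71.4, 69.8 | 75.3% |
| 22.5% / 32.5% (midpoints) | 60.5, 52.7 | 65.4% | 69.2, 65.3 | 73.2% |
| 28% / 44% | 56.2, 43.7 | 59.4% | 67.1, 60.8 | 70.9% |

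At d = 0.45 the none-kept range is 59.8-70.8%, hence about 59-71% overall.

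**3. Recalculate the design effect for smaller clusters, none kept.**
- Low rates: mean cluster size 24 × (1 − 0.19) = 19.4, design effect 1.184, power 72.1%.
- High rates: 24 × (1 − 0.36) = 15.4, design effect 1.144, power 62.7%.

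**4. Maximum enrolment.** 280 × 0.81 ≈ 227 randomised; 227/2/1.23 = 92.3 effective per arm. In the order low, midpoint, high dropout:
- half kept: 82%, 80%, 78%;
- none kept: 78%, 73%, 67%.

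**5. Detectable difference.** At the midpoint rates with none kept (60.5 and 52.7), 80% power by the t-test needs d of about 0.53. That is 0.53 × 1.250 ≈ 0.67 periods, against the 0.56 planned for.

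**6. The measure behind the SD.** The power inputs count toxicology-negative tests. The endpoint in Section 9.5.1 also requires that the participant reports no illicit opioid use in the period. An SD for that composite is not given.

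**The case against.** The strongest objection concerns size. A reader might infer that the plan's own dropout rates imply power of 59-71%. The documents do not support that. The rates describe leaving the intervention and are given for secondary outcomes; Sections 9.5.2 and 9.6 define intervention retention by an active buprenorphine prescription. Section 8 separates discontinuing the group from withdrawing from the study and, with limited exceptions, expects outcome assessments to continue after group termination. Section 5.1 asks selected participants who miss a group to test by video within 24 hours. Section 9.1 adds payments and engagement calls, and Section 6.2.5 a bonus tied to completing at least 90% of oral fluid screens. Late leavers contribute some of the six periods. All of this stands, so the none-kept figures are a bound.

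The design effect may also be conservative. About 24 people per month across both arms is about 12 per arm-specific group. If that group were the cluster at the same ICC (an assumption), the design effect would be 1.11 and complete-data power about 83%; with half of the dropouts' information kept, power would be about 80%, 78% and 75%. That would restore some margin, but the plan chose the cohort of 24 deliberately, and power would still vary with dropout. Any precision gained from covariates in the GEE is likewise not counted here.

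Two further inferences go too far. One is that the means and SDs are urine results: Section 9.2 cites the pilot urine data for the choice of window and expresses the means as oral fluid tests. The other is that the SDs are too small because they imply weak within-person correlation: the documents give no correlation against which to judge that.

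**Conclusion.** The statement that the primary outcome is insensitive to dropout is wrong as written. Under multiple imputation with no rule for scoring missing periods, lost data reduce power. At 192 randomised and the plan's design effect of 1.23 there is no margin, since complete-data power is about 79-80%.

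How far power falls cannot be read from the plan, because the missing-outcome rate is not stated. With the intervention-dropout rates taken as an assumption, it is about 71-75% if half of the dropouts' information is kept. The worst case is about 59-71%, or about 63-72% with the design effect recalculated. At the maximum of 280 enrolled, half retention gives about 78-82%, close to the stated power, and full loss gives 67-78%. All these figures use the plan's t-test and its stated means and SDs, which describe toxicology alone and not the composite endpoint.

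**What to change.** In Section 9.2:

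1. Delete the sentence on insensitivity to dropout.
2. Replace the claim of more than 80% with about 80% for complete data at 192 randomised. Add a range over explicitly stated rates of missing primary-outcome data, with the detectable difference for each (for example, d about 0.53, or 0.67 periods, at the midpoint rates with full loss). Label any full-loss figure as a bound.
3. Base the SD on the actual endpoint, a negative oral fluid test together with no self-report of illicit use. The blinded, pooled SD of the composite count from data already collected would serve.

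The cost is protocol and SAP wording and one blinded calculation. No extra enrolment and no change to the analysis is proposed. The downside is that the stated power becomes less favourable.
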